The effect of deep neuromuscular blockade with Sugammadex reversal on shoulder pain of elderly patients undergoing Robotic Prostatectomy: A single-center double-blinded randomized controlled trial

Principal Investigator: [name] M.D.

Co – Principal Investigator: [name] M.D.

Collaborators: [name] M.D.

The effect of deep neuromuscular blockade with Sugammadex reversal on shoulder pain of elderly patients undergoing Robotic Prostatectomy: A single-center double-blinded randomized controlled trial	
Objectives	
Primary: To compare the effect of deep neuromuscular blockade with Sugammadex reversal versus moderate neuromuscular blockade with neostigmine reversal (standard of care) on postoperative shoulder pain.
 
Secondary: To assess the effect of deep neuromuscular blockade with Sugammadex reversal versus moderate neuromuscular blockade with neostigmine reversal on intraoperative insufflation pressures, perioperative recovery and morbidity for robotic prostatectomy.

Hypothesis	
 1. Elderly patients undergoing robotic prostatectomy who receive continuous deep neuromuscular blockade and its reversal with Sugammadex will have adequate surgical exposure with lower insufflation pressures which will be associated with lower postoperative shoulder pain, less morbidity and a faster recovery when compared to patients receiving moderate neuromuscular blockade. 2. The adoption of continuous deep neuromuscular blockade combined with lower insufflation pressures during robotic prostatectomy will have the most significant effects for patients with multiple comorbidities, such as obesity, age greater than 65, history of congestive heart failure, chronic obstructive pulmonary disease, chronic renal insufficiency, diabetes mellitus, peripheral vascular disease and sarcopenia.
Study Design	Single-center randomized controlled double-blind trial. Patients will receive either the Deep Neuromuscular Blockade (DNMB group) with Sugammadex reversal or Moderate Neuromuscular Blockade (MNMB group) with neostigmine reversal.
Number of Patients	100
Site	M. D. Anderson Cancer Center
Duration of Study	December 2017 to December 2019
Duration of Patient Participation	Until postoperative day 7 or discharge
Primary Endpoints	Incidence of postoperative shoulder pain

Secondary Endpoints	
 1. Quantitative grading of Shoulder Pain using Visual Analog Scale (VAS) for pain score 2. Cumulative intraoperative insufflation pressure (mmHg min) during the surgery 3. Subjective grading of quality of surgical exposure expressed by surgeon at end of case using Surgical Rating Scale (Martini, Boon, Bevers, Aarts, & Dahan, 2013) 4. Readiness to discharge from the PACU as determined by a modified version of the DASAIM discharge criteria scoring system to be completed at 15, 45 and 90 minutes after admission to the PACU 5. Degree of PONV per Visual Analog Scale and number of episodes of emesis per nurse in PACU 6. Length of ICU & Hospital stay, 30-Day Mortality and Readmission Rate 7. Measures of organ dysfunction and perfusion by the Postoperative Morbidity Survey (De novo need for oxygen supplementation, ability to tolerate an enteral diet, oliguria or Acute Kidney Injury, Delirium or new neurological deficits) and postoperative lactate 
Exploratory Outcomes:
 
 1. Optional: Incidence of residual muscle relaxation upon admission to PACU as defined by TOF ratio <0.9, if TOF-Watch® SX is available 2. Optional: Subgroup analysis on elderly patients with comorbidities including laboratory evidence of sarcopenia (creatinine/cystatin c ratio)
Inclusion Criteria	
 1. Patients 65 years of age or older 2. Patients having robotic prostatectomy 3. Written informed consent
Exclusion Criteria	
 1. Patient with known hypersensitivity to Rocuronium, Sugammadex or its components 2. Patients with severe renal insufficiency, defined and confirmed by an estimated creatinine clearance equal or lower than 30 mL/min 3. Patients with history of severe liver disease, defined as and confirmed by elevated ALT and AST greater than 1.5 times the Upper Limit of Normal along with Albumin less than 3 OR INR 1.5 or greater per institutional laboratory.

1. Background

Along with other minimally invasive techniques, the use of robotic laparoscopic surgical techniques require smaller incision sites, are often associated with lower intraoperative blood loss, postoperative pain and shorter recovery when compared with open techniques. (O'Neil, et al., 2016) (Sert, et al., 2016) The use of **insufflation pressure** (IP) required to maintain adequate pneumoperitoneum during robotic surgery can have numerous deleterious effects that are directly correlated with higher pressures (10-15 mmHg or more). These effects include lower respiratory compliance and higher inspiratory pressures, impaired cardiac function, systemic and portal venous stasis, hypercoagulopathy, decreased urine output, decreased organ perfusion and postoperative pain. Shoulder pain is common following laparoscopic abdominal surgery and is thought to be caused by irritation of the diaphragm by the carbon dioxide used for abdominal insufflation. (Fredman, Jedeikin, Olsfanger, Flor, & Gruzman, 1994) The intraoperative maintenance of deep **neuromuscular blockade** (NMB) has the advantage of potentially decreasing the insufflation pressure required by the surgeon to maintain adequate visualization. (Staehr-Rye, et al., 2014) (Koo, et al., 2016) (Kim, Lee, Lee, Min, & Yoo, 2016) By lowering the patients' cumulative exposure to pressurized carbon dioxide pneumoperitoneum, it is possible to decrease the incidence of shoulder pain during the recovery period. (Kim, Lee, Lee, Min, & Yoo, 2016) (Madsen, et al., 2016) Historically, the practice of maintaining deep continuous neuromuscular blockade was limited because excessive NMB would prevent timely extubation of the patient at the end of surgery.

Several studies have demonstrated decreased morbidity from laparoscopic surgery with the use of deep neuromuscular blockade (DNMB). Using data from laparoscopic colorectal surgery, patients in the DNMB vs. moderate NMB (MNMB) group had IP of 9.3 +/- 1.3 vs. 12.0 +/- 0.5 mmHg group respectively. The DNMB group had lower Numeric Rating Scale (NRS) pain scores [2.3(0.6) to 2.9(0.3)], incidence of shoulder pain (3.3% to 25.8%; a reduction of 87%) Gas Passing Time in hours [40(11.3) to 64(31)] and estimated blood loss (20.2 +/- 13.7 vs 60 +/- 95.3 mL). (Kim, Lee, Lee, Min, & Yoo, 2016) In another study which focused on 99 patients undergoing laparoscopic hysterectomy, 28.6% of the DNMB group (IP 8mmHg) vs. 60% in the MNMB group (IP 12mmHg) experienced shoulder pain. (Madsen, et al., 2016) Robotic surgery may differ from conventional laparoscopic surgery in that the duration of surgery is often more prolonged and the patient may be maintained in different positions (steep Trendelenburg or reverse Trendelenburg), both of which may increase the physiologic effects of pneumoperitoneum.

Sugammadex is a gamma cyclodextrin which directly encapsulates steroid NMB agents such as Vecuronium and Rocuronium thus allowing for safe, rapid and more complete reversal of muscular paralysis. (Flockton, et al., 2008) (Geldner, et al., 2012) With the use of Sugammadex, it is now possible to maintain a continuously deep level of muscular relaxation while also extubating the patient at the end of the operation in a safe and efficient manner. (Carron, Baratto, & Ori, 2016) (Ledowski, et al., 2014) (Duvaldestin, et al., 2010)

The Train of Four (TOF) ratio (or TOFR) is a technique for monitoring the degree of blockade by non-depolarizing neuromuscular blocking agents at the nicotinic acetylcholine receptors (neuromuscular junction). An electrical stimulus is applied by transcutaneous nerve stimulator as a group of four stimuli. The quantity and quality of muscular response to nerve stimulation correlates with the degree of neuromuscular blockade. The number of muscular responses to stimulation (TOF count) of 4, 3, 2 and 1 correlates with approximately 75%, 85%, 90% and 95% neuromuscular blockade. The TOF ratio of T4/T1 is a more objective and sensitive method to quantify the degree of neuromuscular blockade calculated by comparing the strength of muscular response of the last TOF stimuli compared to the first. It was previously thought that a

TOFR greater than 0.7 indicated sufficient neuromuscular recovery for extubation. Evidence now suggests that one can have an increased risk of upper airway obstruction and aspiration due to residual neuromuscular blockade with a TOFR less than 0.9, though more prospective studies are needed.

Elderly patients compared to the general population may receive more benefit from the reversal of NMB with Sugammadex as opposed to neostigmine but more prospective studies are needed. In a large retrospective study of 1444 patients, those who had an age greater than 60 and an ASA score of 3 or 4 had a small but significantly higher incidence of postoperative pulmonary complications when treated with neostigmine compared to Sugammadex. (Ledowski, et al., 2014) Additional investigation may identify subgroups within the elderly population who are the highest risk for complications of elevated insufflation pressures or residual neuromuscular blockade.

While there is no universal age which defines the elderly, we chose the age of 65 years or greater to be our threshold based on the Phase 3 trial which demonstrated the safety and efficacy of Sugammadex in the elderly population. Overall, 150 patients were treated and had at least one post-baseline efficacy assessment; 48 were aged 18-64 yr (adult), 62 were aged 65-74 yr (elderly), and 40 were aged 75 yr or older (old-elderly). The geometric mean time (95% confidence interval) from Sugammadex administration to recovery of the TOF ratio to 0.9 increased with age, from 2.3 (2.0-2.6) min (adults) to 2.9 (2.7-3.2) min (elderly/old-elderly groups combined). Recovery of the TOF ratio to 0.9 was estimated to be 0.7 min faster in adults compared with patients aged 65 yr or older ($P = 0.022$). Sugammadex was well tolerated by all patients. (McDonagh DL, 2011)

One possible subgroup that may receive the greatest benefit from the use of Sugammadex are cancer patients with sarcopenia and sarcopenic obesity. Cancer cachexia affects 60-80% of patients with advanced cancer and is associated with increased morbidity and mortality. (Baracos, 2011) Though criteria for cancer cachexia has traditionally varied, an international panel of cachexia experts recently agreed upon a common definition which includes recent weight loss, BMI and sarcopenia. Among 1,077 cancer patients, those classified as cachectic, as defined by weight loss greater than 5% over the last 6 months or greater than 2% with a BMI less than 20 kg/m², had a shorter median survival than for non-cachectic patients. (139 versus 269 days; $P < 0.001$) (Blum, 2014) Among cancer patients to receive chemotherapy, those with sarcopenia had a mortality hazard ratio of 5.19 when controlled for BMI, age and tumor stage. (Gonzalez, 2014)

A laboratory indicator of sarcopenia is the creatinine to cystatin c ratio, which can account for the majority of individual variability of total body muscle mass and has been used to detect sarcopenia and sarcopenic obesity. (Kim, et al., 2016) Cystatin C also has greater prognostic value than creatinine. (K Suzuki, 2015) (Y Otaki, 2015) (Graf, 2015) (Wannamethee, 2015)

The Postoperative Morbidity survey is a 9-point scale used to systematically assess short-term morbidity and multi-organ dysfunction following surgery. (Bennett-Guerrero, et al., 1999) (Davies, et al., 2013) It has been shown to have good reliability and validity with an association with greater hospital length of stay in the general population and increased mortality in the elderly. (Howes, et al., 2015)

2. Hypotheses

2.1 Elderly patients undergoing robotic prostatectomy who receive continuous deep neuromuscular blockade and its reversal with Sugammadex will have adequate surgical exposure with lower insufflation pressures which will be associated with lower postoperative shoulder pain, less morbidity and a faster recovery when compared to patients receiving moderate neuromuscular blockade.

2.2 The adoption of continuous deep neuromuscular blockade combined with lower insufflation pressures during robotic prostatectomy will have the most significant effects for patients with multiple comorbidities, such as obesity, age greater than 65, history of congestive heart failure, chronic obstructive pulmonary disease, chronic renal insufficiency, diabetes mellitus, peripheral vascular disease and sarcopenia.

3. Objectives

3.1 Primary: To compare the effect of deep neuromuscular blockade with Sugammadex reversal versus moderate neuromuscular blockade with neostigmine reversal (standard of care) on postoperative shoulder pain.

3.2 Secondary: To assess the effect of deep neuromuscular blockade with Sugammadex reversal versus moderate neuromuscular blockade with neostigmine reversal on intraoperative insufflation pressures, perioperative recovery and morbidity for robotic prostatectomy.

4. Study Design

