4.3. Exploratory Outcomes

4.3.1. Optional: Incidence of residual muscle relaxation upon admission to PACU as defined by Train-Of-Four (TOF) ratio <0.9, if TOF-Watch[®] SX is available

4.3.2. Optional: Subgroup analysis on elderly patients with comorbidities including laboratory evidence of sarcopenia (creatinine/cystatin c ratio)

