4.5. Eligibility

4.5.1. Inclusion Criteria:

- Patients 65 years of age or older
- Patients having robotic prostatectomy
- Written informed consent

4.5.2. Exclusion Criteria:

- Patient with known hypersensitivity to Rocuronium, Sugammadex or its components
- Patients with severe renal insufficiency, defined and confirmed by an estimated creatinine clearance equal or lower than 30 mL/min, per institutional laboratory.
- Patients with history of severe liver disease, defined as and confirmed by elevated ALT and AST greater than 1.5 times the Upper Limit of Normal along with Albumin less than 3 **OR** INR 1.5 or greater per institutional laboratory.

Patients will be identified when scheduled for Robotic Prostatectomy. Eligible subjects will be approached before scheduled surgery to obtain Informed Consent. Consent will be obtained by Investigator, Co-Investigator and/or Collaborators; the process will be documented in EPIC.

After Informed Consent is obtained, we will collect Demographics, Laboratory Test results of interest for the study, Concomitant Medications taken within 30 days prior surgery and Neoadjuvant Chemotherapy if any.

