4.8. Sample Size Justifications

For 99 patients undergoing laparoscopic hysterectomy, 28.6% of the DNMB group (IP 8mmHg) vs. 60% in the MNMB group (IP 12mmHg) experienced shoulder pain. (Madsen, et al., 2016)

Using the data from the aforementioned study, a sample size of 48 per group will enable the study 88% power to detect the decrease in the rate of postoperative shoulder pain from 60% for the control group to 28.6% for the group with deep Neuromuscular Blockade and Sugammadex, assuming a two-sided type I error rate of 0.05 using a two-group Chi-square test (nQuery Advisor 7.0). Postoperative shoulder pain is defined as any shoulder pain recorded before the discharge from PACU. We predict that the typically increased length of robotic surgery in combination with potentially lower insufflation pressures (6-7mmHg) may result in an even greater difference between the two groups. We want to factor in a 4% drop-out rate, therefore, we will enroll a total of 100 patients.

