4.9. Analysis Plans

Patients' demographic information, laboratory test results and concomitant medications, including neoadjuvant chemotherapy at baseline will be analyzed, with data summarized in tables listing the distributions of the variables along with the number of subjects per treatment arm in order to assess comparability. Patients' information on post-operative shoulder pain, nausea, vomiting, intubation and measures from Postoperative Morbidity Survey will be collected. The Fisher's exact test or Chi-square test will be applied to assess the association between two categorical variables. We will summarize the distribution of average and cumulative intraoperative insufflation pressure, Post Anesthesia discharge DASAIM scores, length of ICU and hospital stay by each treatment. We will use the student t-test or the Wilcoxon rank sum test to compare continuous variables between two different patient groups. Logistic regression will be utilized to assess the effects of patient prognostic factors, comorbidities and treatment on postoperative shoulder pain and postoperative morbidity.

Adverse event (AE) data will be summarized by frequency tables. The association between the types and severity of AE and the treatment will be evaluated.

5. Study Drug Information

Since both Sugammadex and Neostigmine are FDA approved, Insert recommendations and Institutional Standards will be followed for all study agents.

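### Hypothesis 2.2 predicts the largest effect in patients with multiple comorbidities, but no specified analysis compares the treatment effect between comorbid and other patients (inexpensive exploratory improvement)

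*Combined protocol and SAP*

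**What the plan says.** Hypothesis 2.2 states that the intervention "will have the most significant effects for patients with multiple comorbidities, such as obesity, age greater than 65", followed by several cardiac, pulmonary, renal, metabolic and vascular conditions and sarcopenia. It names no endpoint and no effect scale. The objectives in 3.1 and 3.2 do not mention effect modification.

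The Background gives the motive: "Additional investigation may identify subgroups within the elderly population who are the highest risk for complications of elevated insufflation pressures or residual neuromuscular blockade" and "One possible subgroup that may receive the greatest benefit from the use of Sugammadex are cancer patients with sarcopenia and sarcopenic obesity".

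Two places in the plan could bear on 2.2:

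- Section 4.9: "Logistic regression will be utilized to assess the effects of patient prognostic factors, comorbidities and treatment on postoperative shoulder pain and postoperative morbidity".
- Section 4.3.2, under exploratory outcomes: "Optional: Subgroup analysis on elderly patients with comorbidities including laboratory evidence of sarcopenia (creatinine/cystatin c ratio").

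Neither gives an interaction term, a definition of multiple comorbidities or a reference group. Section 4.3.2 also names no outcome.

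Three further passages matter for a remedy. Eligibility (4.5) requires "Patients 65 years of age or older". The baseline list in 4.5 says "we will collect Demographics, Laboratory Test results of interest for the study, Concomitant Medications taken within 30 days prior surgery" and does not name the comorbidities. Section 4.8 fixes the primary outcome: "Postoperative shoulder pain is defined as any shoulder pain recorded before the discharge from PACU".

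**The concern.** A hypothesis that the effect is largest in one kind of patient can be examined only by comparing effects between kinds of patient. A logistic model with treatment and comorbidities as main effects estimates one common treatment odds ratio. An analysis confined to comorbid patients estimates the effect there and says nothing about whether it is larger than elsewhere. Following either section as written would leave 2.2 unanswered.

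The practical risk lies in how 4.3.2 might be carried out. If p-values were computed separately in comorbid and other patients, significance in the first group alone could be read as support for 2.2 even when the benefit is the same in everyone.

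Two wording points affect any such analysis. Age above 65, one of the characteristics listed in 2.2, is met by every eligible patient except those aged exactly 65, so it separates almost no one. The sarcopenia ratio is creatinine over cystatin C in 4.3.2 and its reciprocal in 6.2.6.

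**Working it through.** **Inputs from 4.8.** 48 per group, control rate 0.60, deep-block rate 0.286, two-sided 0.05, chi-square test.

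**Assumed, because the documents do not give them.** The share of comorbid patients, the number of conditions per patient, and a 60% control rate at every comorbidity level.

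**Stated power.** The mean rate is 0.443. z = [0.314 × √48 − 1.96 × √(2 × 0.443 × 0.557)] / √(0.6 × 0.4 + 0.286 × 0.714) = 1.198, giving power 0.885. Exact enumeration of the uncorrected chi-square test gives 0.886. The stated 88% reproduces.

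**Separate subgroup tests with an identical true effect.** Each subgroup's power comes from exact binomial enumeration at 0.60 v 0.286. The subgroups are independent, so P(only comorbid significant) = power(comorbid) × [1 − power(other)].

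| Per arm, comorbid / other | Comorbid share | Power, comorbid | Power, other | Only comorbid significant |
|---|---|---|---|---|
| 10 / 38 | 21% | 0.269 | 0.801 | 0.054 |
| 14 / 34 | 29% | 0.363 | 0.749 | 0.091 |
| 19 / 29 | 40% | 0.517 | 0.678 | 0.166 |
| 24 / 24 | 50% | 0.630 | 0.630 | 0.233 |

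For example, at 24 / 24: 0.630 × 0.370 = 0.233. With Fisher's exact test, which 4.9 also allows, the four figures are 0.037, 0.079, 0.173 and 0.250. By contrast, a two-sided 5% interaction test points wrongly towards 2.2 in nominally 2.5% of trials. Simulation with a comorbidity count (3,000 trials per setting) gave 2.8-2.9%.

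**Precision of the interaction for shoulder pain.** The model is logit(p) = a + bT + cK + dTK, where T is treatment and K counts six conditions, each present independently with probability q. The deep-block arm averages 28.6%. The SE of d comes from the expected information. The CI factor is exp(1.96 × SE) when d = 0, and exp(d) is the ratio of odds ratios per condition.

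| q (mean conditions) | SE | CI factor | Power, ratio 0.75 | Power, ratio 0.6 | Power, ratio 0.5 |
|---|---|---|---|---|---|
| 0.1 (0.6) | 0.591 | 3.19 | 0.076 | 0.126 | 0.183 |
| 0.2 (1.2) | 0.444 | 2.39 | 0.096 | 0.188 | 0.288 |
| 0.3 (1.8) | 0.387 | 2.14 | 0.111 | 0.234 | 0.360 |

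If conditions cluster (assumed correlation 0.15), the power range is 9-48%.

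A two-level split gives a similar picture. Suppose the whole 31.4-point effect falls in comorbid patients, half the sample, and there is none elsewhere. Then SE = √(0.4442/24 + 0.48/24) = 0.196 and 0.314/0.196 = 1.60, so power is 0.36. At a 20% share it is 0.25.

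**Risk difference by level.** Half-width = 1.96 × √(0.4442 / n per arm), with 0.4442 = 0.24 + 0.2042. At 0, 1 and 2 or more conditions:

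- q = 0.1: 26, 32 and 56 points
- q = 0.2: 37, 30 and 32 points
- q = 0.3: 55, 34 and 25 points

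The smallest strata hold about 5.5 patients per arm (48 × 0.114 with two or more at q = 0.1; 48 × 0.118 = 5.6 with none at q = 0.3). The normal approximation is poor there.

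**Why both scales.** The design odds ratio is (0.286/0.714)/(0.6/0.4) = 0.267. Held constant, it gives a risk difference of 31.4 points at a 60% control rate. At a 20% control rate the treated rate is 6.3% and the difference 13.7 points. Because 2.2 names no scale, an odds-ratio interaction alone could mislead.

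**The case against.** The strongest reply is that the plan leaves the comparison unspecified rather than excluding it. Section 4.9 does not rule out an interaction, and many readers take a subgroup analysis to include a contrast between groups. The analysis is labelled both optional and exploratory, the objectives claim no effect modification, and the sample size rests on the primary comparison alone. All of this stands, and it limits the point to an inexpensive improvement. It does not supply an analysis that answers 2.2, one of only two stated hypotheses.

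A reader might infer that the trial is likely to report a spurious subgroup benefit. The documents do not support that. They never say that separate tests will be run in both groups, and read literally 4.3.2 covers comorbid patients only, so no contrast in significance would arise. A reader might also extend the table: shares of 60%, 71% and 79% give 33%, 48% and 59%. The two highest need more comorbid patients than the count model implies. For two or more conditions it gives 11%, 34% and 58% at means of 0.6, 1.2 and 1.8. No prevalence is stated, so the high figures cannot be put forward as expected.

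It is also fair to say that the added estimate will rarely be decisive, and that any comorbidity measure is a matter of choice. Separate tests would use the same data and hide that imprecision; an interval shows it. Finally, the reciprocal sarcopenia ratio carries the same information for a cut-off once its direction is stated, so that part is a wording correction.

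**Conclusion.** The point holds as a modest one: 2.2 asserts effect modification, and neither 4.9 nor 4.3.2 specifies a comparison that addresses it. The 5-23% figure is conditional on separate tests in both groups, a common true effect at the design rates, and an assumed comorbid share of about 20-50%. The interaction power of 8-36% rests on independent conditions averaging 0.6 to 1.8 per patient and a flat 60% control rate, and applies to shoulder pain only. A null interaction would not refute 2.2. Nothing here touches the primary comparison, the total of 100 patients or the 88% power.

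**What to change.** 1. Label 2.2 hypothesis-generating.
2. In 4.9, add one treatment-by-comorbidity interaction to each logistic model already planned, for shoulder pain (as defined in 4.8) and for postoperative morbidity, marked exploratory. State the binary form of the morbidity outcome, since 6.2.6 records nine domains on four days.
3. Fix a single comorbidity measure before unblinding. One reasonable choice is an unweighted count of the clinical conditions in 2.2 (diabetes, obesity, heart failure, COPD, peripheral vascular disease, renal insufficiency), leaving out age above 65.
4. Report the interaction estimate with its 95% CI, and the risk difference with a CI at each comorbidity level (for example 0, 1, and 2 or more), in place of within-subgroup p-values. Use a small-sample interval where strata are small.
5. If sarcopenia is examined, use the same interaction approach in a separate model, and write the ratio in the same direction in 4.3.2 and 6.2.6.
6. Confirm that the listed conditions, with a definition of obesity, are recorded at baseline.

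The cost is a few sentences in 4.9, a label on 2.2 and one corrected ratio. Section 4.9 already intends to model comorbidities and 8.8 mentions medical history in the records, so any condition not captured prospectively can probably be abstracted. Sample size, alpha and the primary test do not change. The price is an imprecise estimate, and an unweighted count treats all conditions as equal.
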